## **9.5 DATA SOURCES**

The study will mainly include the recording of new data through a web based system for data collection. Data will be collected by the study doctors as they occur according to standard clinical practice in the approximate visiting schedule indicated above.

Source (primary) patient data related to their medical and IPF history will be collected by the investigators from the patient's medical files/records and will be documented in the relevant eCRF section.

Data regarding treatment modifications, concomitant treatments, study related routine clinical assessments, adverse events (ADRs) and survival status will also be collected. If a patient withdraws early from the study, they will be contacted via telephone at the end of the Study in order to evaluate their survival status. Another follow-up assessment should be performed if possible (unless reason for discontinuation is erroneous enrolment of the patient into the study at baseline), and data should be entered on the eCRF of the next planned visit unless the patient has actively withdrawn consent for any kind of future contacts.

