Name of active ingredient: Not applicable			
Protocol date: 29 August 2016	Study number: 1199.252	Version/Revision: 1.10	Version/Revision date: 22 February 2018
Research question and objectives:	
The main objective of this IPF registry is to gain further knowledge on the characteristics, management, progression and outcomes of patients with IPF as treated under real-world, clinical practice conditions in Greece.
 
More specifically, this registry is going to:
 

• Provide a comprehensive clinical picture for IPF

• Track access to health care and cost of caring for IPF patients over time

• Examine the implementation of treatment guidelines [2] used on patients diagnosed with IPF, according to the existing diagnosis guidelines [1]

 
Characterization of patients on different treatments
		
Study design:	
National, multi-center, observational disease registry based on new data from a significant sample size of IPF patients in Greece.
 
Patients will be followed up for 2 years and information will be collected during this time period. This is a non-interventional study and primary data collected during study visits will be used.
		
Population:	
About 300 patients are going to be included in the study in a consecutive manner, coming from seven (7) Centers in Greece – University Pulmonology Clinics & Reference Centers of Public Hospital Setting – that follow up around 70% - 80% of IPF patients within the Greek territory from April 2017 to April 2019.
 
To be eligible for participation in the study patients must fulfill ALL the inclusion criteria and NONE of the exclusion criteria that are listed below:
 
Inclusion Criteria
 

• Newly diagnosed (less than 6 months) or patients previously diagnosed with IPF (more than 6 months prior to baseline visit), based upon the consensus statement jointly issued by ATS/ERS/JRS/ALAT in 2011 (see Annexes 6 and 7 on HRCT and histological criteria in Annex 6).

- Exclusion of other known causes of ILD (e.g., domestic and occupational environmental exposures, connective tissue disease, and drug toxicity)

- Evaluation of IPF with HRCT or combinations of HRCT and surgical lung biopsy, if available

		

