## **8. RESEARCH QUESTION AND OBJECTIVES**

The overall objective of the present IPF Registry is to gain further insight on the characteristics, management, disease progression and the outcomes of patients with IPF, as diagnosed and treated under real-world, clinical practice conditions in Greece.

More specifically, this registry will be used to:

- Provide a comprehensive clinical picture of IPF
- Track access to health care and cost of caring for IPF patients over time
- Examine the implementation of treatment guidelines [2], used on patients diagnosed with IPF, according to the existing diagnosis guidelines [1]
- Characterization of patients on different treatments

Furthermore, this project aims to provide information regarding survival and mortality causes, IPF exacerbations as well as IPF patient co-morbidities including myocardial infarction, CNS infarction, other arterial thromboembolic events, deep vein thrombosis, hemorrhage, gastrointestinal perforation and pulmonary hypertension (please refer to [Annex 3](#)). In addition, data regarding IPF patient hospitalization will be collected and evaluated with regards to potential respiratory causes, and there will be documentation of treatment patterns and economic aspects. Patients will be followed up for 2 years and information regarding IPF treatment changes since the last visit will be collected.

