### **9.3.2 Withdrawal Criteria**

The patients reserve the right to withdraw consent at any time during the study, without the need for justification and without any impact on their future treatment and care.

Withdrawal of consent means that the patient does not wish or cannot continue to participate in the study any more.

The reasons for withdrawal may include the following:

- Patient or legally accepted representative withdraws informed consent for participation in the study.
- Inclusion or possible participation in any clinical trial, any time within the follow up period of the study, in which the patient has been exposed or is going to be exposed to an investigational product (pharmaceutical product or medical device) or intervention.
- The patient was erroneously included in the registry
- Decision of the investigator/physician
- Important deviation/divergence from the protocol.

The Clinical Monitor at BI or BI's designees must be immediately notified if a patient is discontinued prematurely for any of the instances reasons cited above.

Patients that withdraw from the study should be asked about the reason(s) for withdrawal and the occurrence of adverse events, and should be examined and evaluated by the investigator according to the procedures that are defined in the Final Visit (unless reason for discontinuation is erroneous enrolment of the patient into the study at baseline and unless patient has actively withdrawn consent for any kind of future contacts).

If the patient specifically withdraws consent for future contact about the collection of further information, there will be no such contact whatsoever. However, it is possible to collect information regarding their survival status, if they are publicly available.

The investigators also reserve the right to remove a patient from the study, if according to their clinical judgment this is the necessary for the patient's welfare.

If a patient is removed or withdrawn from the study for any reason, the date, vital status and reason must be documented in the relevant section of the electronic Case Report Form (eCRF).

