### **9.3.3      Study Visits**

The registry is scheduled to run for 4 years in total (2 years recruitment + 2 years follow up) (April 2017 to April 2021).

During the follow up period, data will be collected on standard clinical visits which usually are scheduled around: 3-months (+/- 1 month), 6-months (+/- 1 month), 12-months (+/- 2 month), 18-months (+/- 2 month) and 24 months (+/- 2 months), until the end of participation in the study. In case of events, unscheduled visits may be required.

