- Clinical events and hospitalizations especially due to: (acute) respiratory worsening, including pneumonia, exacerbations of IPF, occurrence of pulmonary or cardiovascular complications, pulmonary rehabilitation, pulmonary embolism, pneumothorax, or cardiac failure
- Management of IPF and physician contacts

During follow up visits (prospectively until up to 2 years at least from the inclusion) 3-months (+/- 1 month), 6-months (+/- 1 month), 12-months (+/- 2 month), 18-months (+/- 2 month) and 24 months (+/- 2 months), documentation of events (or last follow up visit) will be carried out. The collection of data will be performed during standard clinical practice visits (i.e. visits should not be performed via telephone contact). In a special event where the physical presence of the patient is not possible, e.g. in case of temporary inability of the patient to visit the expert center, this visit could be performed through telephone contact and this should be recorded in patient's history. Every effort should be made, however, to ensure that the next visit will be performed as planned by the patient in person. If this is not possible the patient will be censored for the rest of the study. Patient will be followed up until death, lung transplantation, consent withdrawal or end of study, whichever comes first and will be censored if one of the events occurs. The following data will be documented:

- Clinical course of IPF (e.g. regarding symptoms, lung functionality, exercise ability, if available)
- Vital status
- Physical and vital signs examination
- Cardiopulmonary exercise testing (6-minute walk distance and CPET, if performed)
- Autoimmune Biomarker results (No additional specimen will be collected. Only already existing data will be used from exams that have been performed according to the routine clinical practice of the physicians)
- Risk of bleeding and thrombosis
- Outcomes of interest (such as acute respiratory worsening, exacerbations, hospitalization due to any cause and due to IPF). Please, refer to [Annex 3](#)
- Recording of therapeutic algorithms (change/complement/interrupt treatment) and non-pharmacological treatment (e.g. start of LTOT, new listing for lung transplantation)
- Physician's clinical rating of the probable course of IPF (stable, slow or rapid

progression)

- Assessment of treatment intensity, frequencies and resource use for pharmacoeconomic analyses for the treatments described under 11.3

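### Survival status is to be traced after withdrawal, but Protocol 9.4 censors at withdrawal and the SAP does not say which rule governs the Kaplan-Meier curves

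*Protocol*

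**What the plan says.** **Tracing after withdrawal.** Protocol 9.5, on patients who withdraw early: "they will be contacted via telephone at the end of the Study in order to evaluate their survival status". It also asks for a further follow-up assessment where possible. Protocol 9.3.2 requires vital status to be documented at withdrawal and, where the patient refuses further contact, still permits publicly available survival information.

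**Censoring.** Protocol 9.4: "Patient will be followed up until death, lung transplantation, consent withdrawal or end of study, whichever comes first and will be censored" if one of these events occurs. The same paragraph censors, for the rest of the study, a patient who has had a telephone visit and then cannot return in person.

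**Length of follow-up.** The Abstract says "Patients will be followed up for 2 years and information will be collected during this time period", and section 8 agrees. Section 9.4 has "prospectively until up to 2 years at least from the inclusion" and also names the end of study, without saying whether that means the patient's last visit or the close of the registry. Vital status is collected for everyone at visits up to month 24 (Table 1). The end-of-study call is written for early withdrawals only.

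**Analysis.** SAP section 4 adds Kaplan-Meier curves to the descriptive tables. The SAP gives no censoring rule, no time horizon and no use for status obtained after withdrawal. SAP 6.6 leaves patients with an incomplete date of death out of the time-to-event analysis.

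**The concern.** Survival and causes of death are stated aims (Protocol section 8). The protocol plans to collect deaths after withdrawal and also states a rule under which the curve would not use them. The SAP leaves the choice open, so it could be made once the data are known.

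The choice matters if leaving is related to prognosis, which the text makes plausible. Section 9.3.2 lets the investigator remove a patient for the patient's welfare, and section 9.4 censors patients who cannot attend. In a progressive lung disease, inability to attend may well follow decline. Kaplan-Meier assumes that censored patients have the same later risk as those who stay.

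The opposite choice, using traced status to the end of the study, has its own problem if completers stop at month 24: the later part of the curve then describes withdrawn patients only.

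**Working it through.** **1. The plan's own figures.** Recruitment of 24 months plus follow-up of 24 months is 48 months, April 2017 to April 2021, so the four-year duration reproduces. In Table 2, the asymptotic half-width at n = 300 and 50% is 1.96 × √(0.25/300) = 5.66 points, matching 44.34% to 55.66%. The documents give no event count or precision for survival.

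**2. Time at which status is known.** Data collection ends on 5 June 2021. A withdrawn patient enrolled in April 2017 is traced at about 50 months, and one enrolled in April 2019 at about 26 months. A completer's last planned assessment is at 24 (± 2) months. The excess is about 2 to 26 months.

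**3. Effect of censoring at withdrawal.** Inputs:
- Median survival m = 30 months, the middle of the 2 to 3 years in Protocol 7.4. Applying it from enrolment is an assumption.
- Exponential survival with hazard λ = ln 2/m = 0.02310 per month. Assumption.
- A share W leaving by month 24 in the absence of death, with hazard w = −ln(1 − W)/24. Assumption.
- Death hazard after leaving = h × λ. Assumption.

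True survival at month 24 is

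S(24) = e^(−24(λ+w)) + w·e^(−24hλ)·[1 − e^(−24a)]/a, with a = λ + w − hλ.

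The first term is patients alive who never left; the second is patients alive after leaving. If leaving censors, Kaplan-Meier estimates e^(−24λ) = 57.4% whatever h is.

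| W | h | w | Stayed, alive | Left, alive | True S(24) | Censoring at withdrawal | Difference |
|---|---|---|---|---|---|---|---|
| 10% | 1.5 | 0.00439 | 51.7% | 5.0% | 56.7% | 57.4% | 0.7 |
| 20% | 2 | 0.00930 | 45.9% | 8.7% | 54.7% | 57.4% | 2.7 |
| 20% | 1 | 0.00930 | 45.9% | 11.5% | 57.4% | 57.4% | 0 |

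In the second row the expected share leaving before death is w/(λ + w) × (1 − 0.459) = 0.155, or about 46 of 300. Of these 8.7%, about 26 of 300, are alive at month 24, so about 20 die between withdrawal and month 24.

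Simulation over medians of 24 and 36 months and withdrawal of 10% to 30% gives a bias of about 1 to 4 points at h = 2, about 2 to 7 points at h = 3, and none at h = 1.

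**4. Effect of using traced status without a cap.** Survival at month 24 is correct if tracing is complete. After that only withdrawn patients are at risk, so the curve falls at rate hλ. For m = 30, W = 20%, h = 2:
- estimate at month 36: 0.547 × e^(−12 × 2 × 0.02310) = 0.547 × 0.574 = 0.31;
- truth: 0.459 × e^(−12 × 0.02310) + 0.087 × 0.574 = 0.348 + 0.050 = 0.40 (0.39 if withdrawals continue beyond month 24).

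Simulation with the same W and h gives 0.237 against 0.318 for a median of 24 months, and 0.377 against 0.462 for 36 months.

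**5. Counting traced deaths and capping everyone at month 24.** With complete tracing, the 24-month estimate equals the simulated truth in every scenario.

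**The case against.** The strongest reply is that this is a descriptive registry without hypotheses, its curves are only to illustrate survival, and the gap is one of wording. Several parts of that stand.

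- **Size.** An overstatement of 0.7 to 2.7 points is smaller than the 5.7-point half-width at n = 300. Withdrawal share and hazard ratio appear nowhere in the documents. The quoted median runs from diagnosis and, the protocol says, may be an underestimate, while the cohort includes patients diagnosed more than 6 months earlier.
- **Mitigation.** Protocol 9.10 plans to describe dropouts and compare them with the remaining patients. That would show whether they differ but would not correct the curve.
- **Scope of the rule.** Section 9.4 names consent withdrawal. Section 9.3.2 describes withdrawal of consent as including patients who cannot continue, and lists other reasons such as investigator decision or trial entry. Whether those censor is a matter of reading.

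Some stronger readings are tempting but unsupported:

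- *Known deaths are discarded and follow-up is unequal.* These are alternatives. If withdrawal censors, later status cannot lengthen anyone's follow-up in the curve; if it is used, those deaths are not lost. No text says that traced deaths are dropped; that follows only if 9.4 is applied.
- *Either reading overstates survival.* Using traced status without a cap lowers late survival if those who leave do worse.
- *The call will find only the living.* This is conjecture, and section 9.3.2 allows public sources.
- *The end dates conflict.* Section 9.3.3 has "2 years recruitment + 2 years follow up) (April 2017 to April 2021" and section 6 has 5 June 2021. The two months fit the +2-month window of the last visit.
- *Completers should be followed to June 2021.* Two-year follow-up is the stated design. Extending it is a preference, and an amendment would need approval by the hospital boards (Protocol 10.1).

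**Conclusion.** The concern holds as an unresolved conflict between a stated censoring rule and a stated plan to collect later survival status. Applied as written, Protocol 9.4 leaves planned mortality data out of the survival curve and invites informative censoring. The overstatement of 24-month survival is about 0.7 to 2.7 points for 10% to 20% withdrawal and hazard ratios of 1.5 to 2, zero if leaving is unrelated to prognosis, and larger if the link is stronger. Using traced status to study end without a cap gives a sound 24-month figure if tracing is complete, but a misleading curve beyond it. All sizes rest on assumed withdrawal, hazard ratio and exponential survival, and on completers stopping at about month 24; they show direction and rough scale only. This is a near-free improvement, worth making before the survival analysis is run.

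**What to change.** State the rule once in the SAP and align Protocol 9.4 with it:

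1. For the survival analysis, do not censor at withdrawal or non-attendance when later vital status is known and its use is permitted.
2. Count deaths and known-alive time up to month 24 from enrolment, however the information was obtained.
3. Censor untraceable patients at the date last known alive.
4. Truncate every patient at month 24, so that traced and untraced patients share one horizon.
5. At the end-of-study call already planned, or from public sources, record the full date of death or the date last known alive. A complete date also keeps the patient from being excluded under SAP 6.6.
6. Reword the 9.4 sentence so that death is clearly the event; as written, it is listed among the events at which patients are censored.

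The cost is SAP and protocol wording plus a date field at a contact already planned. Any protocol amendment goes to the hospital boards as usual. No extra follow-up of completers is needed.

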## **9.6 STUDY SIZE**

This observational study will be analyzed using descriptive statistics following standard statistical and epidemiological methods. Approximately 300 patients are expected to be included in the study in a consecutive manner between April 2017 and April 2019 from the participating sites according to the feasibility procedure of the sites.

The number of included patients as well as the duration of the study is not defined by a formal sample size and power calculation, but is based mainly on the availability of eligible IPF patients as well as patient population in the selected sites.

[Table 2](#) describes the expected precision for the description of a proportion, according to different sample sizes. Note that within Table 2 the first interval relates to an asymptotic 95% confidence interval and the second interval relates to an exact 95% confidence interval (i.e. The Clopper-Pearson interval).

Table 2. Precision of estimates for binary parameters

(Sub) group size	Proportion				
	50%	40%	30%	20%	10%
50	(36.14%, 63.86%)	(26.42%, 53.58%)	(17.30%, 42.70%)	(8.91%, 31.09%)	(1.68%, 18.32%)
	(35.53%, 64.47%)	(26.41%, 54.82%)	(17.86%, 44.61%)	(10.03%, 33.72%)	(3.33%, 21.81%)
100	(40.20%, 59.80%)	(30.40%, 49.60%)	(21.02%, 38.98%)	(12.16%, 27.84%)	(4.12%, 15.88%)
	(39.83%, 60.17%)	(30.33%, 50.28%)	(21.24%, 39.98%)	(12.67%, 29.18%)	(4.90%, 17.62%)
200	(43.07%, 56.93%)	(33.21%, 46.79%)	(23.65%, 36.35%)	(14.46%, 25.54%)	(5.84%, 14.16%)
	(42.87%, 57.13%)	(33.15%, 47.15%)	(23.74%, 36.86%)	(14.69%, 26.22%)	(6.22%, 15.02%)
300	(44.34%, 55.66%)	(34.46%, 45.54%)	(24.81%, 35.19%)	(15.47%, 24.53%)	(6.61%, 13.39%)
	(44.20%, 55.80%)	(34.41%, 45.79%)	(24.87%, 35.53%)	(15.62%, 24.98%)	(6.85%, 13.97%)

For continuous endpoints, precision of estimates will depend on parameter specific assumptions on mean and standard deviation. A generic display as given for binary endpoints is therefore less appropriate.

## 9.7 DATA MANAGEMENT

The registry will include the collection of new data that will be recorded in an existing web based database in a consecutive manner (electronic case report form, eCRF) as well as transferring already existing data to the system from medical charts. The patients will be identified by subject identification number, site number, and study identification number.

Investigators will enter the data of their patients directly into an internet-based electronic case record form. At data entry, plausibility checks (e.g., range checks, conditional checks, etc.) will be performed. Data will be entered in the eCRF system by the study personnel at the Investigator's site, according to the Investigator Instructions Manual. Data entered in the eCRF system will be automatically saved to a central database and changes tracked to provide an audit trail. When data have been entered, reviewed and edited, the Investigator shall sign the e-CRF electronically as per the agreed project process and data will be locked to prevent further editing.

Query management will be performed through built-in query management functionality that will be incorporated into the eCRF.

Prior to the onset of data management activities, a detailed data management plan (DMP) will be issued describing the procedure to be followed for processing all collected study data in order to ensure they are valid, complete and accurate for statistical analysis. In addition, aiming at ensuring the expected quality of data, a thorough data cleaning session will be applied. When all data have been properly validated and the quality control procedure has been completed, a declaration of database lock will take place so that it can be confirmed that all important actions have been properly performed. In addition, prior to database lock, and prior to the initiation of any statistical analysis activities a comprehensive statistical analysis plan (SAP) will be drafted. The SAP will also include information regarding the statistical software(s) to be used for the analysis of the study data and any data imputation methods that may be applied.

## **9.8 DATA ANALYSIS**

[figure not shown]
### **9.8.1 Main Analysis**

The objective of this registry is neither to confirm nor to reject any predefined hypothesis; therefore the nature of the statistical analyses will be exploratory and descriptive.

Continuous variables will be listed as median with interquartile and other percentages, and as mean value with standard deviation (SD), along with minimum and maximum values (depending on the underlying distribution). Categorical values will be listed as absolute and relative frequencies. All events during follow up will be described as incidence rates with 95% confidence interval (CI).

Stratified analyses will be performed among newly diagnosed patients (< 6 months) as well as patients that were diagnosed in the past ( $\geq 6$  months). In case of conflicting results those of the newly diagnosed will be the decisive. Due to limited number of patients and population heterogeneity, no comparison between treatments can be done and no causal relationship conclusion can be derived (no hypothesis testing). Statistical analyses will be performed with IBM SPSS Statistics (Version 19.0).

If it was not avoidable to select patients from sites with other ongoing registries, patients enrolled in other registries in parallel need to be analyzed separately. In case of difference the results for the BI registry patients are decisive.

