### **7.2 INCIDENCE AND PREVALENCE**

Overall, epidemiological data on the incidence and prevalence of IPF are limited, as stated in the consensus statement issued by ATS/ERS/JRS/ALAT [1].

In a population-based study from New Mexico, the incidence of IPF was estimated at 10.7 cases per 100,000 per year for men and 7.4 cases per 100,000 per year for women [1]. In the UK, an overall incidence rate of only 4.6 per 100,000 person-years was reported, however, with an estimated increase by 11% annually between 1991 and 2003 (not attributed to aging of the population or increased ascertainment of milder cases) [4]. In the USA, based on a large database of healthcare claims in a health plan, the incidence of IPF was estimated between 6.8 and 16.3 per 100,000 persons [5].

Prevalence estimates for IPF, as assessed in England, Japan, New Mexico, Norway, Italy and Greece, have varied widely from 1,82 to 35,51 cases per 100,000 in the general population [2, 6-9, 26]. The wide range in these numbers is likely explained by the previous lack of uniform definition used in identifying cases of IPF, as well as by differences in study designs and populations [1]. In the USA, a recent analysis based on healthcare claims yielded a prevalence estimate between 4.0 - 42.7 per 100,000 persons depending on the case definition used [5]. Another study from the US, estimated a prevalence of 58.7 per 100,000 (95% CI 56.3-61.2) for IPF, after correction of the estimate for its PPV after chart review [27]. It is unknown if the incidence and prevalence of IPF are influenced by geographic, ethnic, cultural, or racial factors [1]. In Italy, a relevant study from N. Agabiti, M. A. Porretta, L. Bauleo, A. Coppola, et al, conducted at Lazio region, concluded that IPF incidence and prevalence in this large central-southern Italian region are strikingly similar to those derived from the hospital and general medicine databases of northern Europe and the United States. At the same time, this study stated that IPF incidence is more likely driven by industrialization, urbanization and western lifestyles than the ethnic variables characterizing different European regions [25]. In 2016, another study conducted in Lombardy, the most populous region of Italy, estimated the annual incidence and prevalence at 7.5 and 25.6 per

[figure not shown]

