## **7.4 NATURAL COURSE**

Data on the natural course of IPF are from retrospective and a few prospective studies, including the placebo arms of clinical trials (limited to short observation periods and by in/exclusion criteria). The previously reported median survival time of 2-3 years from the time of diagnosis could be an underestimate, at least when accounting for patients with preserved lung function. Notably, the natural course is unpredictable for a given patient at the time of diagnosis, while the majority of patients experience steady worsening (slow progression), others remain stable, or have rapid progression of disease [\[10-11\]](#). Acute respiratory worsening either due to secondary complications (e.g. pneumonia, pulmonary embolism, pneumothorax or cardiac failure) or due to unknown reasons (in this case the term acute exacerbation is used) are suggested to occur in about 5-10% annually [\[1\]](#). A recent retrospective review of 461 patients with IPF has found that the 1- and 3-year incidences of acute exacerbations were 14.2% and 20.7%, respectively [\[12\]](#).

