### **3. INTRODUCTION**

“As per ICH E9, the purpose of this document is to provide a more technical and detailed elaboration of the principal features of the analysis described in the protocol, and to include detailed procedures for executing the statistical analysis of the primary and secondary variables and other data in order to support future publications based on IPF patients.

This TSAP assumes familiarity with the Clinical Trial Protocol (CTP), including Protocol Amendments. In particular, the TSAP is based on the planned analysis specification as written in CTP Section 9.8 “Data Analysis”. Therefore, TSAP readers may consult the CTP for more background information on the study, e.g., on study objectives, study design and population, treatments, definition of measurements and variables, planning of sample size, randomization”.

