#### **4. CHANGES IN THE PLANNED ANALYSIS OF THE STUDY**

As described in the study protocol only descriptive analysis will be applied for the purpose of the present study. Further to the summary tables of frequencies and measures of central tendency, Kaplan Meier curves will be produced to illustrate the survival distribution of patients in the study.

Analysis of the baseline characteristics was decided to be performed when all subjects had entered the trial.

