**7.4 PRIMARY ENDPOINT(S)**

[figure not shown]
Only descriptive statistics are planned to be performed in the overall sample as well in the stratified by time of diagnosis subgroups.

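### The SAP does not carry out the protocol's commitment to report follow-up events as incidence rates with 95% CIs, and its two denominator rules for categorical percentages conflict

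*Protocol*

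**What the plan says.** **Events.** Protocol 9.8.1 (Main Analysis) states: "All events during follow up will be described as incidence rates with 95% confidence interval (CI". The same section asks for stratified analyses by time since diagnosis. Protocol 9.4 sets the end of observation: "Patient will be followed up until death, lung transplantation, consent withdrawal or end of study, whichever comes first". Time at risk will therefore differ between patients.

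SAP 3 states that "the TSAP is based on the planned analysis specification as written in CTP Section 9.8". SAP 4, the section for changes to the planned analysis, adds one analysis: "Kaplan Meier curves will be produced to illustrate the survival distribution of patients in the study". It also gives the timing of the baseline analysis and lists nothing else. For the primary endpoints SAP 7.4 says: "Only descriptive statistics are planned to be performed in the overall sample as well in the stratified by time of diagnosis subgroups". SAP 7 gives mean, SD, median, minimum and maximum for continuous data, and counts with percentages for categorical data. SAP 7.8.1 counts subjects with adverse events.

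**Denominators.** SAP 6.6 restricts summary statistics to subjects with available information and takes unknown data out of the total for each variable. SAP 7 takes percentages over all subjects in the set, with or without a value, unless something else is specified. Neither section refers to the other. Protocol Table 1 lists variables to be recorded if available, so some missing values are expected.

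**The concern.** A SAP should be more specific than the protocol section it implements. Here it is less specific. From its text a programmer could not tell whether first or all events are counted, when time at risk starts and stops, or how an interval is computed. Followed literally, it yields percentages of patients with an exacerbation, hospitalisation or haemorrhage, with no interval and no allowance for unequal follow-up. The Kaplan-Meier curves deal with survival only and leave out the non-fatal outcomes of Annex 3.

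The denominator conflict is a smaller point of the same kind: two analysts following the same SAP could report different percentages from the same data.

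**Working it through.** **1. Textual comparison**

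| Item | Protocol 9.8.1 | SAP 4, 7, 7.4, 7.8.1 |
|---|---|---|
| Measure for follow-up events | Incidence rate | Counts and percentages; Kaplan-Meier for survival only |
| Time at risk | Not defined | Not mentioned |
| 95% CI | Required | Not mentioned |
| Listed as a change in SAP 4 | – | No |

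**2. The plan's own precision figure.** Protocol Table 2 gives, for 20% at n = 300, an asymptotic interval of 15.47% to 24.53% and an exact one of 15.62% to 24.98%.
- Asymptotic: 0.20 ± 1.96 × √(0.20 × 0.80 / 300) = 0.20 ± 0.0453, which agrees.
- Clopper-Pearson with x = 60 gives 15.62% to 24.98%, which agrees.

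All 40 intervals in the table reproduce to within rounding (largest deviation 0.005 points). The table is correct, but it covers proportions only and says nothing about the precision of a rate.

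**3. What a percentage leaves out.** The documents give no event count or time at risk, so these are assumed: 60 first events in 300 patients and mean time at risk of 1.8, 1.5 or 1.2 years. The rate is events / patient-years (PY). Exact Poisson limits are χ²(0.025; 120)/2 = 45.79 and χ²(0.975; 122)/2 = 77.23, each divided by PY.

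| Mean time at risk | PY | Percentage | Rate per 100 PY (95% CI) |
|---|---|---|---|
| 1.8 y | 540 | 20.0% | 11.1 (8.5–14.3) |
| 1.5 y | 450 | 20.0% | 13.3 (10.2–17.2) |
| 1.2 y | 360 | 20.0% | 16.7 (12.7–21.5) |

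**4. How much deaths could move a crude percentage, from the protocol's figures.** Protocol 7.4 reports, from a retrospective review, that "the 1- and 3-year incidences of acute exacerbations were 14.2% and 20.7%, respectively". With a constant hazard these give r = −ln(1 − 0.142) = 0.153 per year, or r = −ln(1 − 0.207)/3 = 0.077 per year. On survival the same section says: "The previously reported median survival time of 2-3 years from the time of diagnosis could be an underestimate". Medians of 3 and 2 years give death hazards h = ln 2/3 = 0.231 and ln 2/2 = 0.347 per year. The crude 24-month percentage is r/(r + h) × (1 − exp(−2(r + h))):
- r = 0.153: 21.4% (3-year median) and 19.4% (2-year median), a difference of 2.0 points.
- r = 0.077: 11.5% and 10.4%, a difference of 1.1 points.

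Withdrawal and transplantation are left out of this calculation.

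**5. Is the hazard constant?** The two exacerbation figures say not. Taken together, they give a hazard after year 1 of ln(0.858/0.793)/2 = 0.039 per year, against 0.153 in year 1. Ignoring deaths, the two-year first-event rate is then:
- probability of an event: 1 − 0.858 × exp(−0.039) = 0.175
- mean time at risk: 0.142/0.153 + 0.858 × (1 − exp(−0.039))/0.039 = 1.77 years
- rate: 0.175/1.77 = 9.9 per 100 PY, against 15.3 over one year.

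So a rate is also an average that depends on the length of follow-up.

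**6. Denominators.** For 60 positives in 300, the SAP 7 default gives 60/300 = 20.0%. SAP 6.6 gives 60/270 = 22.2%, 60/240 = 25.0% or 60/210 = 28.6% with an assumed 10%, 20% or 30% missing.

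**The case against.** **Nothing was withdrawn.** The SAP presents itself as an elaboration of Protocol 9.8, and a rate is a descriptive statistic, so 9.8.1 may still govern. The display plan dated 24 April 2020 was not available, and SAP numbering skips 6.4, 7.6 and 9. This stands against the inference that the sponsor decided to drop the rates, which the documents do not show. It does not supply the missing specification, and the SAP cites the display plan only for the baseline visit.

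**Incidence may mean a proportion.** Table 2 uses binomial intervals, Protocol 7.4 expresses incidence as percentages, and the ENCePP checklist marks measures of effect, with deaths per person-years among its examples, as not applicable. That reading is possible. However, Protocol 7.2 uses the term for person-time ("an overall incidence rate of only 4.6 per 100,000 person-years was reported"), and even on the binomial reading the required 95% CI is absent from the SAP.

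**The distortion is small.** A reader might infer that crude percentages would badly mislead when newly and previously diagnosed patients are set side by side. The protocol's figures do not support this. Moving median survival from 3 to 2 years shifts the percentage by about 1 to 2 points, against a half-width of about 4.5 points for 20% even at n = 300. The calculation also assumes a constant hazard that those figures contradict, and a rate is not free of dependence on follow-up length either. This objection stands in full.

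**Readers could compute their own interval.** From counts and denominators they could compute a binomial one, but not the interval for a rate.

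**SAP 6.6 overrides SAP 7.** The SAP 7 default yields where something else is specified, and 6.6 may be that specification. But 6.6 is not limited to any type of variable, and the SAP does not say which rule prevails.

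**Conclusion.** The point holds as a mismatch between protocol and SAP. Protocol 9.8.1 promises incidence rates with 95% CIs for all follow-up events. The supplied SAP text specifies no rate, time at risk or interval, and SAP 4 does not declare the difference. This is more than missing detail, because following the SAP literally gives an output other than the one promised. Its practical size is the loss of the interval and of any adjustment for time observed: under the assumed inputs, one figure of 20.0% covers rates from 11.1 to 16.7 per 100 patient-years. No claim of serious bias between the two diagnosis strata follows.

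The denominator conflict is real but secondary. It amounts to 5 points for 60 positives at an assumed 20% missing. The true missingness is not stated in the documents.

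The textual finding rests on the SAP as supplied. If the display plan already defines rates and CIs for follow-up events, the remaining task is to bring them into the SAP text.

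**What to change.** **Events.** In SAP 7.4, for each Annex 3 outcome separately, overall and by newly or previously diagnosed, report:
- the number of patients with an event and the total time at risk;
- first events per 100 patient-years with a 95% CI, for example exact Poisson.

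Count time from enrolment to the first event or end of follow-up. For chronic conditions such as pulmonary hypertension, exclude patients who already have the condition at baseline, since they are not at risk of a first event. Add an exception to SAP 6.7 so that events recorded at unscheduled visits count: SAP 6.7 leaves such visits out of the primary and secondary endpoints, while Protocol 9.3.3 foresees that events may require them.

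Check the eCRF for onset dates of acute exacerbation, other arterial thromboembolism, gastrointestinal perforation and haemorrhage. Annex 3 lists none for these, and the Annex 5 haemorrhage entry covers previous bleeding only. Where there is no onset date, use the visit interval.

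State that each rate averages over follow-up and may change with its length if the hazard is not constant. If rates are not wanted, list and justify the departure in SAP 4.

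**Denominators.** State the same policy in SAP 6.6 and SAP 7. Variables with a missing or Unknown category, including the Yes/No/Unknown medication items of Annex 4, use subjects with known values as denominator, with the missing or unknown count shown. Whole-set denominators apply only to items with no unknown category, such as adverse events.

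**Cost.** SAP wording, modest programming and the eCRF date check. No new data collection is needed, because the visit interval can stand in for a missing onset date.
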